2.1 Primary Objective

The primary objective of the continuation of URECA to age 17 is to determine the wheezing, asthma and atopy phenotypes in minority children growing up in poor urban neighborhoods as they develop from birth through adolescence.

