10.4 Analysis Plan

10.4.1 Primary Analysis of Primary Objective

The purpose of the primary analysis in the fourth phase of URECA will be to identify wheezing and asthma phenotypes in the children through the age of 17 years. Furthermore, we will identify risk factors for the asthma phenotypes related to environmental exposures, immune responses and biomarkers, weight and fitness status, and airway and environmental microbiota.

Using the extensively and longitudinally characterized URECA cohort, we will:

1. Categorize URECA subjects into already described early life patterns of wheezing (Tucson Children's Respiratory Study, Avon Longitudinal Study of Parents and Children, Prevention and Incidence of Asthma and Mite Allergy) and development of atopic disorders (Manchester) to determine if these patterns are indeed observed among inner-city American children.
2. Using longitudinal data obtained from the URECA cohort through the age of 17 years, we will perform a cluster analysis to identify patterns of wheezing, allergic sensitization and lung function over time. In URECA the comprehensive longitudinal measurements within a child allow the application of techniques such as latent class analysis where periods have the greatest impact on the development and maintenance of asthma through the teen years. In particular, symptoms, exacerbations, allergy, immunologic measures, BMI, fitness, psychosocial factors and objective measurements of lung function, spirometry, eNO and IOS will define clusters of asthma phenotypes based on a combination of these variables. We will consider latent class analysis and other clustering techniques to identify phenotypes in URECA V.

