To identify endotypes, we will use a sparse multinomial logistic regression model. Variables for these models include the DNA methylation and expression modules (Aim 1), and environmental exposures (e.g. viral infections, allergens, microbes, tobacco smoke). Thus, the model will represent endotypes by mapping from biological states and environmental exposures to clinical phenotypes. In a sparse model, the learning algorithm is biased towards selecting a relatively small number of variables. Thus, although we will include a moderately large number of candidate variables in the models, only a sufficient number of variables to distinguish the phenotypes are selected. We will use well established sparse learning methods, such as LASSO and elastic net, which are well suited to high-dimensional data sets that include many potentially irrelevant variables.

We will next identify biomarkers for predicting respiratory allergy and asthma phenotypes that we observe at ages 11 and 15. This analysis will start with subjects clustered according to the phenotypes that we defined in Aim 3.1 and will proceed by inferring functions composed from individual early-life biomarkers that are predictive of the phenotype an individual subject will exhibit. Sparse multinomial logistic regression models will be used to evaluate early life biomarkers. The candidate predictor variables for these models will include (i) demographics, (ii) clinical variables such as wheeze frequency, (iii) gene expression measurements from nasal epithelial cells, and (iv) DNAm measurements from nasal epithelial cells. Aside from demographics, these variables will come from measurements taken during the first three years of life.

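### Early-biomarker model (10.4.3): demographics, and as written also early wheeze, can be both predictor and ingredient of the phenotype, so accuracy would overstate forecasting of later disease

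*Protocol*

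**What the plan says.** Four places in the protocol matter.

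- **Predictors (10.4.3, biomarker paragraph).** The candidates are demographics, "ii) clinical variables such as wheeze frequency", and gene expression and DNA methylation from nasal epithelial cells. On timing: "Aside from demographics, these variables will come from measurements taken during the first three years of life".
- **Target (same paragraph).** "This analysis will start with subjects clustered according to the phenotypes that we defined in Aim 3.1". The preceding sentence describes the task as "predicting respiratory allergy and asthma phenotypes that we observe at ages 11 and 15".
- **How the target is built (10.4.3, opening paragraph).** Latent class mixed models summarise the trajectory of each variable. The variables that characterise those trajectories (symptoms, sensitization, lung function and BMI are the examples) then enter a Gower distance matrix together with other predictors, demographics among them, and children are clustered on it. The approach is said to resemble that of the 7- and 10-year data sets. Section 3.2.1 describes the 7-year phenotypes as resting on trajectories of symptoms, sensitization and lung function.
- **Time span.** The primary objective (2.1) concerns phenotypes in children "growing up in poor urban neighborhoods as they develop from birth through adolescence". Section 1.2, under Aim 1, describes phenotypes and exposures as collected longitudinally from birth. Section 10.4.1 uses data through age 17 to "perform a cluster analysis to identify patterns of wheezing, allergic sensitization and lung function over time", without a start age.

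Nothing removes ages 0-3 from the Aim 3.1 phenotypes, wheeze from the predictors, or demographics from either side.

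**The concern.** A variable that helps to form the groups will help to predict the groups, whether or not it says anything about later disease. Here the prediction has a purpose: section 1.2 (Aim 3) wants biomarkers that identify endotypes early, and 10.4.3 speaks of the phenotype that a child will go on to show. If wheeze at ages 0-3 is a segment of the trajectory that defines the phenotype, part of the apparent accuracy is the model reading back its own input. Demographics raise the same problem.

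Cross-validation does not cure this. The phenotype of a held-out child already contains that child's early wheeze and demographics, so the overlap travels with the label into every fold.

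The second thing at stake is how the molecular markers look. If overlapping clinical variables carry much of the signal, expression and methylation may seem to add less than they do for disease after age 3.

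**Working it through.** **The plan's own figure.** The protocol gives no accuracy, power or effect size for this model. Its only relevant number is the cohort (10.5): 442/609 = 72.6%, which rounds to the stated 73%. The simulations use n = 442.

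**Text side by side.**

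| Variable | Predictor? | In the target? |
|---|---|---|
| Demographics | Yes | Yes, stated: part of the Gower matrix |
| Wheeze, ages 0-3 | Yes | Symptom trajectories are in; start age not stated; birth is the natural reading |
| Nasal expression and methylation | Yes | Not listed |

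**Does the overlap bias accuracy?** All data below are assumed. The quantity of interest is

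gap = AUC (phenotypes built with ages 0-3) − AUC (phenotypes built from ages 4-17 only),

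where AUC is the mean one-versus-rest value.

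*A. Symptoms only, one-stage k-means.* 200 cohorts per setting, 17 yearly scores, 4 or 6 groups, ages 1-3 independent of ages 4-17. Early wheeze supplies 3 of 17 inputs. AUC was 0.69-0.74 with overlap and 0.53-0.54 without. A test of no association rejected in 97-100% and 3-5% of runs. Giving early scores twice the spread raised the AUC to 0.84-0.86.

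*B. Several domains, one-stage k-means, L1 multinomial model, 5-fold cross-validation.* Early wheeze is one of seven clustering inputs. There are 20 biomarkers, 3 of them true, and 5 clusters, with 8-12 cohorts per setting. Here rho is the correlation (or carry-over) between early and late wheeze.

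| Setting | With 0-3 | Ages 4-17 | Gap |
|---|---|---|---|
| No information (rho 0, effect 0) | 0.656 | 0.452 | 0.204 |
| rho 0, effect 0.35 | 0.690 | 0.520 | 0.170 |
| rho 0.3, effect 0.35 | 0.714 | 0.544 | 0.170 |
| rho 0.6, effect 0.35 | 0.694 | 0.617 | 0.077 |
| rho 0.3, effect 0.5, direct | 0.724 | 0.601 | 0.123 |
| rho 0.6, effect 0.5, direct | 0.704 | 0.646 | 0.058 |
| rho 0.3, effect 0.5, only through early wheeze | 0.675 | 0.487 | 0.188 |
| rho 0.6, effect 0.5, only through early wheeze | 0.689 | 0.601 | 0.088 |

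The gap is positive in all eight settings, from 0.058 to 0.204, although the AUCs are cross-validated. It shrinks as early wheeze becomes genuinely informative.

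*C. Closer to the planned two-stage method.* 60 cohorts, early wheeze independent of later wheeze. A wheeze trajectory class, three other domain classes and two demographics enter a Gower distance with medoid clustering, so wheeze is one of six inputs. AUC was 0.55 with overlap (4 or 6 groups) and 0.53 without, a gap of 0.02. No association was rejected in 52% of runs, against 3-5%. The other domains were assumed independent of wheeze, which favours dilution.

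**Are biomarkers lost from the sparse model?** In B, for phenotypes built with ages 0-3:

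| Biomarker effect | True biomarkers kept (of 3), wheeze offered vs not |
|---|---|
| Direct, five settings | 2.88-3.00 vs 2.62-3.00 |
| Only through early wheeze, rho 0.3 | 1.83 vs 1.83 |
| Only through early wheeze, rho 0.6 | 2.33 vs 2.83 |

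Loss appears in one setting of seven. Summed coefficients shrank in six of seven (for example 1.35 vs 2.04) and rose in one (1.08 vs 0.98). They also shrank in some settings without overlap (1.27 vs 1.76), so shrinkage is partly the usual effect of adding a correlated predictor.

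**The case against.** **The overlap for wheeze is inferred.** No section states the start age of the Aim 3.1 symptom trajectory. Section 2.1 is the primary objective, and 10.4.1 gives only an end age. The wording about ages 11 and 15 could mean phenotypes defined at those ages. This stands as a limit: a reader might infer that the protocol commits to trajectories from birth, and it does not. But no separate age-11 or age-15 phenotype is defined, and the next sentence makes the Aim 3.1 clusters the target. For demographics no inference is needed.

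**The larger simulated AUCs come from another algorithm.** This stands. A reader might take 0.69-0.74, or 0.84-0.86, as the inflation to expect in this cohort. The documents do not support that: those runs cluster symptoms alone, and the doubled spread has no basis in the text. Under the two-stage version the gap was small, though detectable.

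**Early recognition of a life-course pattern is legitimate.** If the phenotype is a pattern from birth, classifying a child at age 3 partly from early wheeze is not an error, and the protocol promises no accuracy figure. This stands for classification. It does not stand for forecasting, which is how 10.4.3 and Aim 3 frame the product.

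**The detail may belong elsewhere.** Section 10.1 sends mechanistic aims to separate analytic plans, which could fix the window. But this protocol itself fixes target, predictors, predictor window and model class, and the problem arises from that combination.

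**Conclusion.** The point holds in conditional form. Demographics are on both sides of the early-biomarker model by the protocol's own description. Wheeze at ages 0-3 is on both sides on the natural reading, and as written nothing prevents it. Accuracy reported as a forecast of later disease would then be biased upward, and cross-validation would not remove the bias.

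The size cannot be derived from the documents. It depends on how much weight symptoms carry in the clustering and on how far early wheeze truly predicts later disease. Under assumed data the AUC gap ran from about 0.02 (two-stage, independent domains) to about 0.20 (one-stage, no real information). Simulation B rests on only 8-12 cohorts per setting, so it shows direction rather than precise size.

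A reader might also infer that true biomarkers are crowded out of the sparse model. That is not shown: their added value may be understated, but loss was not consistent, and the protocol also allows elastic net. Nor is the trial's main result at risk. This is an exploratory step, and the primary and secondary analyses are unaffected.

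**What to change.** For this model only:

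1. State the age window of the Aim 3.1 symptom trajectories, and what is meant by phenotypes observed at ages 11 and 15.
2. Form the target phenotypes from data after the third birthday, and leave demographics out of that clustering.
3. Keep early wheeze plus demographics as the benchmark model, and report the gain from expression and methylation markers over it.

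If the birth-to-17 phenotypes are kept as target, either drop the overlapping predictors (early wheeze and other symptom variables, and demographics) or describe the result as classification of a life-course pattern, not as forecasting.

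The cost is wording and one extra clustering run on stored data. The downside is that the later-onset phenotypes may differ slightly from the birth-to-17 ones, and the quoted accuracy may be lower.

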10.5 Sample Size Considerations

The sample size for the URECA cohort is determined by the original recruitment, and retention to this point (442 subjects at age 14 years, which represents 73% of the original 609 recruited subjects) has been excellent. This sample size enabled identification of phenotypes at 7 and 10 years of age.

11 Quality Control and Quality Assurance

Training of study staff will be conducted prior to beginning any new procedures. All staff members will be required to complete certification and quality control in all applicable study procedures as outlined in the URECA V MOP for ICAC-07. The site principal investigator and study coordinator(s) will be responsible for ensuring that all procedures are performed according to the protocol. Periodic reviews of procedures will be conducted by the study coordinator or other trained personnel according to an individual schedule for each staff member that is based on the activities they are responsible for conducting. Details of the quality control plan, including certifications and quality control of study procedures, are provided in the URECA V MOP for ICAC-07.

12 Ethics/Protection of Human Subjects

12.1 The Belmont Report

In accordance with the [FWA00005897](#): "This institution assures that all of its activities related to human subject research, regardless of funding source, will be guided by the ethical principles of The Belmont Report." Additionally, the investigator assures that all activities of this protocol will be guided by the ethical principles of The Belmont Report, 45 CFR 46 and all of its subparts (A, B, C and D).

12.2 Institutional Review Board

A copy of the protocol, informed consent forms, other information to be completed by participants, such as survey instruments or questionnaires, and any proposed advertising/recruitment materials will be submitted to the IRB for written approval.

All subsequent amendments to the protocol, informed consent documents, and other study documentation referenced above must be reviewed and approved by the IRB before implementation. The annual Continuing Review must also be reviewed and approved by the IRB throughout the duration of the study.

The IRB will be notified of SAEs and protocol violations.

12.3 Informed Consent Process

The informed consent and assent forms are a means of providing information about the study to a prospective participant/guardian to allow for an informed decision about participation in the study. The parent or legal guardian of the participating child (or their legally acceptable representative) must read, sign, and date the informed consent form before continuing the study or undergoing any study-specific assessments. Consent materials for participants who do not speak or read English will be translated into Spanish for clinical sites with Spanish-speaking staff.

The informed consent and assent forms will be revised whenever important new safety information is available, whenever the protocol is amended with changes that require re-consent/re-assent by participants, and/or whenever any new information becomes available that may affect participation in the study.

A copy of the informed consent form (and assent form, if applicable) will be given to a prospective participant/caretaker for review. The prospective participant/caretaker will be told that being in the study is voluntary and that he or she may withdraw from the study at any time for any reason.

12.4 Assent Process

All URECA V participants will sign a written assent form as described above.

12.5 Participant Confidentiality

Following Health Insurance Portability and Accountability Act guidelines, a participant's privacy and confidentiality will be respected throughout the study. Each participant will be assigned a

sequential identification number and this number, rather than a name, will be used to collect, store, and report participant information. Data reported in medical journals or scientific meetings will be presented in aggregate for participants as a whole. No individual participant will be identified in any way.

Participant confidentiality will be strictly held in trust by the participating investigators, their staff, and the sponsor(s) and their agents. This confidentiality is extended to cover testing of biologic samples in addition to the clinical information relating to participating subjects.

The study protocol, documentation, data, and all other information generated will be held in strict confidence. No information concerning the study or the data will be released to any unauthorized third party without prior written approval of the sponsor.

The study monitor or other authorized representatives of the sponsor may inspect all documents and records required to be maintained by the investigator, including but not limited to medical records (office, clinic, or hospital) for the participants in this study. The clinical site will permit access to such records.

12.6 Study Discontinuation

There are no study halting rules. However, the study may be discontinued at any time at the discretion of the NIH.

13 Data Handling and Record Keeping

Study data will be entered in a login-secured, web-based electronic data capture (EDC) system. The system operates on all Internet browser platforms and is designed to handle numerous simultaneous studies within a program. Physical, logical, and operational security related to the data is implemented by a network operation center. Additional details regarding the EDC system are provided in the Data Management Plan (DMP) for ICAC-07.

13.1 Data Management Responsibilities

The data management tasks required for this study are a joint responsibility of the SACCC and clinical site staff. The clinical site staff are responsible for collecting and entering study data into the EDC system per the protocol and specific guidelines in the URECA V MOP for ICAC-07, for ensuring the accuracy of these data, and for maintaining and organizing all original source documents and any additional sources of data. The EDC system has been validated and is compliant with Part 11 Title 21 of the Code of Federal Regulations. The site principal investigator is responsible for supervising the data collection and data management processes at the clinical site to ensure the overall quality of the data generated by all clinical site staff. The SACCC is responsible for ensuring the quality of the data at all the clinical sites. The specific responsibilities of the clinical site staff, site principal investigators, and the SACCC are included in the DMP for ICAC-07. All data management activities at the SACCC and clinical sites will be conducted in accordance with the DMP.

13.2 Data Capture Methods

Data will be captured onto paper CRFs for later entry into eCRFs, or directly into eCRFs. The first recording of any information captured for the study will be considered the source document,

which may be, but is not limited to, a medical record, a laboratory or clinical report, a paper CRF, or an eCRF.

The details regarding the electronic verification of all data fields, including univariate and multivariate validation (i.e., range checks and cross-field and cross-form checks), validation of data omission, and query management are listed in the DMP.

13.3 Types of Data

Clinical, demographic, laboratory, and AE data will be collected for this study.

13.4 Source Documents and Access to Source Data/Documents

The clinical sites participating in this study will maintain the highest degree of confidentiality permitted for the clinical and research information obtained from the participants. Medical and research records will be maintained at each clinical site in the strictest confidence. However, as a part of the quality assurance and legal responsibilities of an investigation, the clinical site must permit authorized representatives of the sponsor to examine (and when required by applicable law, to copy) clinical records for the purpose of quality assurance reviews, audits, and evaluations of the study safety and progress. Unless required by the laws that permit copying of records, only the coded identity associated with documents or with other participant data may be copied (and all personally identifying information must be obscured). Authorized representatives as noted above are bound to maintain the strict confidentiality of medical and research information that is linked to individuals. The clinical site will normally be notified before auditing visits occur.

13.5 Timing/Reports

Data will be monitored by staff at the SACCC. Status reports on the progress of the study and data collection will be generated regularly. Reports will be sent to the NIAID project manager and medical officer on a regular basis.

13.6 Study Records Retention

Study documents must be maintained at the clinical site or a local storage facility for at least 5 years following the completion of the study. Study documents that must be retained include all hard copies of CRFs, IRB approval documentation and related correspondence, and signed informed consent forms.

14 Publication Policy

Presentations and publication of the results of this study will be governed by the CAUSE Publication Policy.

Appendix B: Schedule of Procedures/Evaluations

In response to the scheduling challenges posed by COVID-19, the URECA V protocol is written so that many visit activities can shift from one visit to the next. If a participant has consented to additional visits, activities may also be made-up at unscheduled, additional visits.

- Formally scheduled at this visit
- May be conducted at this visit only if missed when last formally scheduled.

	Quarterly Calls	14/15-Year Time Point		16/17-Year Time Point		Methacholine Challenge Visit ²
		Visit A	Visit B	Visit A	Visit B	
Questionnaires¹						
Quarterly Symptom and Exposure Assessment	●	●	●	●	●	
Annual Symptom and Exposure Updates		●	●	●	●	
Comprehensive Stress Assessment (Caretaker and Child)		●	▫	●	▫	▫
Study Procedures^{1,3}						
Allergen Skin Test (e)		●	▫	▫	▫	▫
Bioelectrical Impedance Analysis			●		●	▫
Blood Sample Collection ⁴	●	▫	●	▫	▫	▫
Dust Sample Collection Supply Distribution	●	▫	●	●	▫	▫
Exhaled Nitric Oxide (s)	●	▫			●	▫
Fitness Test			●			
Impulse Oscillometry	●	●			●	●
Induced Sputum (s)				●		
Methacholine Challenge (s)	●	▫				●
Nasal Epithelial Cell Collection			●	▫	▫	▫
Nasal Lining Fluid Collection			●	▫	▫	▫
NicoTest (Urine collection)	●	▫	●	●	▫	▫
Physical Examination	●	▫	●	●	▫	●
Post-Bronchodilator IOS and Spirometry (c)	● ⁵	▫ ⁵			●	▫ ⁶
Pregnancy Test (Urine collection, as applicable)	●	●	●	●	●	●
Spirometry (c)	●	●	●	●	●	●
Tanner Stage	●		▫			▫

¹ Asthma outcomes: (c) core, (s) supplemental, (e) emerging as recommended by NIAID and NHLBI Asthma Outcomes Workshop

² As applicable. Participants who are unable to conduct the methacholine challenge at the 14/15-Year Visit A or Visit B will be asked to come to clinic for a separate visit any time after the participant's 14/15-Year Visit B.

³ Invalid tests or samples that are lost, damaged, or otherwise unusable may be repeated at either an unscheduled visit or the following clinic visit.

⁴ Additional blood may be drawn at any time during the study.

⁵ At the Year 14 visit, bronchodilator reversibility will be performed only if the child does not meet the criteria for performing the methacholine challenge. In this case, the methacholine challenge will be conducted at Year 15. If,

instead, bronchodilator reversibility is missed at Year 14 in favor of the methacholine challenge, reversibility will be done at the Year 15 visit.

⁶ At the standalone Methacholine Challenge Visit, staff will conduct Post-Bronchodilator IOS/Spirometry only when the participant both does not meet ATS guidelines for the Methacholine Challenge and did not perform Post-Bronchodilator IOS/Spirometry at the last formally scheduled instance.
